8.8.7. Medications (2 Weeks, 4-6 Weeks, 3 Months)

Changes to oral or intravenous medications will be recorded.

8.9. Long-term Follow-up (6 monthly)

Subjects will be followed up at 6 Months post-implant and 6 monthly until the study is closed. The following data will be collected during these visits:

- Electrical Testing (Sensing, Impedance, and Pacing tests (see section 8.8.3))
- Save-to-media file
- Medications (see section 8.8.7)
- Photographs of device pocket and sternal incision (see section 8.8.5.2) are recommended if an infection related to the EV ICD System is suspected or previously diagnosed
- Adverse Event assessment

8.10. Unscheduled Visits

An unscheduled follow-up visit is defined as any unplanned visit by the subject to the investigative study site due to the EV ICD system between protocol required visits. Routine visits such as planned visits are not collected.

Emergency department visits are not required to be reported as Unscheduled Follow-up visits as they are not considered investigative study sites.

If an unscheduled visit occurs:

- Document any adverse events and device deficiencies on their associated eCRFs, as applicable.
- Where possible, device interrogation data should be collected via a save-to-media file for subjects at the beginning and end of the visit (initial and final interrogation). Device interrogation data should be sent to Medtronic, with a copy being maintained at the site in the subject's file.
- If electrical testing is conducted, it is recommended that programmer strips are obtained. It is preferred that full programmer strips are obtained real-time while the test is running. A copy of the entire programmer strips will be stored at the site and one full copy will be sent to Medtronic.
- Photographs as recommended (see section 8.8.5.2)

8.11. System Modification

A System Modification will be reported in the event the EV ICD system requires an invasive modification after the initial implant (e.g., explant, replacement, repositioning).

If the system modification involves replacing or repositioning the lead or EV ICD, then all testing and data collection required at Implant and the Pre-Hospital Discharge visit should be repeated, with the following caveat:

- If system modification occurs after initial pre-hospital discharge visit -
 - ECG Holter monitoring is not required
 - Defibrillation testing will be completed per physician discretion. It is recommended that the device is programmed with a 10J safety margin

In the event of a system modification where an EV ICD System remains in the body, the follow up schedule for the subject will remain unchanged. In cases where an EV ICD System is explanted and not replaced with an EV ICD System, the subject will be exited from the study provided any procedure, system or accessory related adverse events are resolved.

8.12. Role of the Sponsor Representatives

Sponsor representatives will provide support as required for the study under supervision of the Principal Investigator, including:

- Provide study training relevant and pertinent to the involvement of personnel conducting study activities and investigator responsibilities, including but not limited to training on the: CIP, informed consent process, data collection tools, and regulations
- Technical support in installing/uninstalling the programmer software into/from the Programmer manually or via the SDN
- Technical support at all study visits under the supervision of the Principal Investigator, including device programming, but no data entry on the eCRF shall be performed by Medtronic personnel or their representatives at sites
- A Medtronic Procedure Expert will support a study investigator at the Implant Visit by proactively providing advice and feedback during the implant procedure, but no tunneling shall be performed by Medtronic personnel or their representatives.

Sponsor representatives may conduct monitoring and auditing activities for this study.

8.13. Assessment of Efficacy

Efficacy of the EV ICD System with regards to defibrillation testing success will be assessed per the primary efficacy objective at the implant visit. In addition, efficacy of antitachycardia pacing (ATP) and asystole pacing will be characterized as part of the ancillary objectives.

8.14. Assessment of Safety

All Adverse Events that are procedure related, system related, accessory related, Holter related, cardiovascular related or serious will be collected throughout the study duration, starting at the time of signing the consent form. Additionally, any device deficiencies related to the EV ICD System will be collected. In addition, an ancillary objective will summarize reported Adverse Events. Further information on the collection of Adverse Events is discussed in Section 10.

8.15. Recording Data

This study will be conducted using the Oracle Clinical Remote Data Capture system (OC RDC). The OC RDC system, which allows the study centers to enter study data into the sponsor's database over a secure internet connection, will be used to capture study required eCRF information. The Principal Investigator or an individual delegated by the Principal Investigator is responsible for entering data for the study on the eCRFs. The Principal Investigator or Sub-Investigator designee is required to approve all data on eCRFs via electronic signature. The data reported on the eCRFs shall be derived from source documents, and any discrepancies shall be explained in writing. The following eCRFs may be considered as source:

- Protocol Deviation
- Device Tracking

Save-to-media files will be collected and stored on USB flash drives at the site. A copy will be submitted to Medtronic via secure and compliant electronic file transfer services (e.g., Clinical Transfer, Kiteworks) and/or mailed via USB.

Programmer printouts will be collected in hard or electronic copy and stored at the site. A copy will be submitted to Medtronic via secure and compliant electronic file transfer services (e.g., Clinical Transfer, Kiteworks) and/or mailed via USB.

Fluoro /radiograph/ CT images are to be stored on a CD/DVD or USB flash drive at the site. A copy will be submitted to Medtronic via secure and compliant electronic file transfer services (e.g., Clinical Transfer, Kiteworks) and/or mailed via USB.

Photographs are to be copied from the camera SD card and saved onto a USB flash drive at the site. A copy will be submitted to Medtronic via secure and compliant electronic file transfer services (e.g., Clinical Transfer, Kiteworks) and/or mailed via USB.

ECG recordings from DR220 are to be copied from the SD card and saved onto the USB flash drive at the site. A copy will be submitted to Medtronic via secure and compliant electronic file transfer services (e.g., Clinical Transfer, Kiteworks) and/or mailed via USB.

8.16. Deviation Handling

A study deviation is defined as an event within a study that did not occur according to the Clinical Investigation Plan or the Clinical Trial Agreement.

Prior approval by Medtronic is expected in situations where the investigator anticipates, contemplates, or makes a conscious decision to deviate. Prior approval is not required when a deviation is necessary to protect the safety, rights or well-being of a subject in an emergency or in unforeseen situations beyond the investigator's control (e.g., subject failure to attend scheduled follow-up visit, inadvertent loss of data due to computer malfunction, inability to perform required procedures due to subject illness).

For medically justifiable conditions which preempt a subject's ability to complete a study-required procedure, it may be permitted to report only one deviation which will apply to all visits going forward. This may also apply for other unforeseen situations (e.g. the subject permanently refuses to complete a study required procedure and the data will not contribute to the primary end point analysis). However, prior approval from Medtronic is required for such situations.

All study deviations must be reported on the Case Report Form regardless of whether medically justifiable, pre-approved by Medtronic, an inadvertent occurrence, or taken to protect the subject in an emergency. In the occurrence of a corrupted device interrogation file, Medtronic may request a deviation to document that a readable interrogation file is unavailable.

Refer to [\[redacted\]](#) for deviation reporting requirements and timeframes for reporting to Medtronic, Ethics Committee and/or regulatory bodies, as required per local law.

Medtronic is responsible for analyzing deviations, assessing their significance, and identifying any additional corrective and/or preventive actions (e.g. amend the Clinical Investigation Plan, conduct additional training, terminate the investigation). Repetitive or serious investigator compliance issues may result in initiation of a corrective action plan with the investigator and site, and in some cases, necessitate suspending enrollment until the problem is resolved or ultimately terminating the investigator's participation in the study. Medtronic will provide center-specific reports to investigators summarizing information on deviations that occurred at the investigational site on a periodic basis.

Examples of study deviations include but are not limited to:

- Failure to obtain proper Informed Consent
- Failure to collect required study data (e.g., required imaging, echocardiograms)
- Inclusion/exclusion criteria not met
- Missing required save-to-media files
- Missing Holter data

8.17. Subject Withdrawal or Discontinuation

Subjects are urged to remain in the study as long as possible but may be exited from the study for reasons such as:

- Subject has completed the study
- Subject lost to follow-up
- Subject death
- Subject did not meet inclusion/exclusion criteria
- Subject chooses to withdraw (e.g., consent withdrawal, relocation to another geographic location)
- Subject does not have or no longer has EV ICD System implanted
- Subject does not pass defibrillation testing prior to pre-hospital discharge
- Investigator deems withdrawal necessary (e.g., medically justified)

A withdrawn subject will be treated according to standard of medical care and will not be replaced. Subjects will be included in the analyses up to the time that consent was withdrawn.

Subjects who had undergone an implant attempt and have an EV ICD System implanted or had their EV ICD System removed without replacement with an EV ICD System may be exited by phone at the end of 30 days once all system and procedure-related AEs are resolved.

The following information is required to be collected at study exit:

- Reason for exit (this should be documented in the Study Exit eCRF and in the subject's medical record)

In the case that the subject is determined to be lost to follow-up, details of a minimum of two attempts and the method of attempt (e.g., one letter and one phone record or two letters) to contact the subject must be recorded. In addition, follow the regulations set forth by the governing Ethics Committee. Upon withdrawal from the study, no further study data will be collected or study visits will occur for the subject.

9. Risks and Benefits

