8.8. Scheduled Follow-up Visits

Subjects will undergo assessments at scheduled follow-up visits to characterize the safety and efficacy of the EV ICD System. These assessments include:

- Electrical Testing per section 8.8.3 (electrical stability and acceptability of pacing threshold and pacing at safety margin)
- Provocative testing per section 8.8.4 (Ensure adequate sensing in ambulatory setting)
- Collection of imaging per section 8.8.5 – (mechanical stability)
- Holter monitoring per section 8.8.2 (on site) and 8.8.6 (24 Hour) – (electrical stability)

Medtronic will provide the target dates and window for each follow-up visit to the implanting center. Follow-up visit windows open on the Window Start date and remain open as defined in Table 7. It is recommended that subjects are scheduled as close as possible to the target date for a given follow-up visit.

Table 7: Scheduled visit windows.

Study Follow-up Visit	Window (Calculated days post-implant procedure)		
	Window Start (days post-procedure)	Target (days post-procedure)	Window End (days post-procedure)
2 Weeks	10	14	21
4-6 Weeks	28	30	49
3 Month	90	90	120
6 Month	180	180	210
12 Month (1 Year)	335	365	395
18 Month	518	548	578
24 Month (2 Year)	701	730	760
30 Month	883	913	943
36 Month (3 Year)	1066	1096	1126
42 Month	1248	1278	1308
48 Month (4 Year)	1431	1461	1491

All subjects with an implanted EV ICD System will remain in the study and be followed at pre-defined study visits until official study closure. After their study participation ends, the EV ICD System will remain implanted and the subject will be provided with standard medical care by their physician.

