#### 7.1.2 Clinical Investigation Plan (CIP) Deviations

Study deviations will result in corresponding Study Deviation eCRFs being completed. These deviations will be summarized with descriptive statistics including, for each type of deviation, how many occurrences there were in the study, and the number of subjects experiencing each type of deviation. Inclusion/exclusion violations will not result in subjects being excluded from analysis of objectives. Of particular importance will be required testing not completed at implant or follow-up.

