### 7.4 Handling of Missing, Unused, and Spurious Data and Dropouts

All available data will be included in the data listings and tabulations. Imputation of values for missing data for primary and secondary efficacy analyses will not be performed. With regard to the safety primary objective, subjects who exit the study prior to experiencing a major system or procedure-related complication will be censored at the date of their exit (in the case of the subject being lost to

follow-up, the subject will be censored at the date of last contact with the subject) in the calculation of any Kaplan-Meier freedom from complication rates.

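### Protocol 8.17 and 8.8 conflict on when an implanted subject may leave the study, so a major complication between exit and day 90 can go uncounted

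*Protocol*

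**What the plan says.** **Retention.** Protocol 8.8 has no eligibility exception: "All subjects with an implanted EV ICD System will remain in the study and be followed at pre-defined study visits until official study closure".

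**Exit.** Protocol 8.17 lists reasons for which a subject may be exited. One is "Subject did not meet inclusion/exclusion criteria", with no timing attached. Later in the same section a separate sentence covers "Subjects who had undergone an implant attempt and have an EV ICD System implanted or had their EV ICD System removed without replacement" by another EV ICD System, and says that they "may be exited by phone at the end of 30 days once all system and procedure-related AEs are resolved".

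**Data after exit.** Protocol 8.17: "Upon withdrawal from the study, no further study data will be collected". Protocol 10.2 likewise ends adverse event follow-up at study exit if that comes before resolution or closure.

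**Eligibility violations.** Protocol 8.16 gives unmet criteria as an example of a study deviation. SAP 7.1.2 says: "Inclusion/exclusion violations will not result in subjects being excluded from analysis of objectives".

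**Primary safety analysis.** The endpoint is a first related major complication within 90 days, inclusive (Protocol 4.1.1 and 12.3.2; SAP 7.9.1.2). The rate is a Kaplan-Meier estimate at 90 days (SAP 7.9.1.4) over all implant attempts (SAP 7.9.1.5). Under SAP 7.4, subjects who exit before a major complication "will be censored at the date of their exit".

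**The concern.** Suppose monitoring finds that an implanted subject breached an exclusion criterion. Under 8.8 the site must keep following that subject. Under 8.17 it may exit the subject. Nothing in the protocol says which rule prevails.

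The choice bears on the primary safety result. Several exclusions in Protocol 7.4 exist because they raise implant or surgical risk: anatomical abnormality including BMI above 40, and comorbidities such as oxygen-dependent COPD. If subjects who breach such criteria leave early, their censoring may be related to their risk of the endpoint, whereas Kaplan-Meier assumes that it is not. SAP 7.1.2 intends these subjects to contribute to the analysis. An early exit keeps them in it but cuts short what they can contribute.

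This is also the first chronic human implant of the system. A subject exited with the system in place is outside study safety follow-up.

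**Working it through.** The plan gives no figure to reproduce. The study is descriptive, with 20 to 35 implants (SAP 6) and no hypothesis (SAP 7.9.1.1). The check is a comparison of the text followed by an illustration.

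**Can 8.17 reach an implanted subject?**
- The list of reasons mixes stages. It includes loss of the system and failed defibrillation testing, so it is not a screening list.
- The reason about failed defibrillation testing states its timing (before pre-hospital discharge). The eligibility reason states none.
- The 30-day sentence names subjects who have the system implanted. Its day 30 falls 90 − 30 = 60 days before the endpoint window closes.

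Read literally, both texts conflict with 8.8.

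**What does an exit do to the estimate?** The Kaplan-Meier rate at day 90 is S(90) = ∏(1 − d/r) over event days, where d is the number of events and r the number at risk. Assumed, not in the documents: one exit at day 30; the exited subject would have had a major complication at day 60; all others are followed to day 90 or to an event.

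| Case | n = 20, followed | n = 20, exited | n = 35, followed | n = 35, exited |
|---|---|---|---|---|
| A. No other events | 1 − 1/20 = 95.0% | 100% | 1 − 1/35 = 97.1% | 100% |
| B. One other subject has an event at day 5 | (19/20)(18/19) = 90.0% | 19/20 = 95.0% | (34/35)(33/34) = 94.3% | 34/35 = 97.1% |
| C. Exited subject's event is at day 5, before exit; no other events | 95.0% | 95.0% | 97.1% | 97.1% |
| D. Exited subject would have had no event; another subject has one at day 60 | 1 − 1/20 = 95.0% | 1 − 1/19 = 94.7% | 1 − 1/35 = 97.14% | 1 − 1/34 = 97.06% |

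Each missed event in A and B costs 1/20 = 5.0 points or 1/35 = 2.9 points. With two or three such subjects and no other events, the followed rates are 90.0% and 85.0% at n = 20, and 94.3% and 91.4% at n = 35. The exited rate is 100% in all four. Moving the exit in case A from day 30 to day 1 also leaves 100%.

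Case C shows that events before exit are kept. Case D shows that exiting a subject who would have stayed event-free lowers the rate slightly.

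**The case against.** **The eligibility reason may be meant for screen failures only.** Subjects are enrolled at consent (Protocol 7.2), criteria are confirmed at baseline (8.5), and 8.5.1 exits unsuitable candidates after the CT scan. Section 8.8 is the specific rule for implanted subjects, and 8.16 already treats unmet criteria as a deviation. This is a fair reading and may be the intended one. A reader might infer that the sponsor plans to exit implanted violators, and nothing in the documents shows that. But the limit is not written, and the 30-day sentence does name implanted subjects.

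**The 30-day sentence may be a drafting slip.** Sections 8.6.7.9 and 8.11 already give exit rules for unsuccessful implants and removed systems, so the sentence may have been meant for those subjects. If its conditions govern every exit of an implanted subject, days 0 to 30 are observed, unresolved related events block the exit, and only about days 31 to 90 are exposed. Section 8.17 does not say whether they do. Related events that first arise after exit are missed on either reading.

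**SAP 7.1.2 is not contradicted.** This stands. A reader might infer that violators fall out of the safety rate. They do not: a censored subject stays in the analysis set, and in the risk set until exit.

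**The informativeness is assumed.** This stands in part. No document gives the complication risk of ineligible subjects, and some criteria (geographic stability, concurrent studies) have little to do with implant risk. Others are expressly about it.

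**No pass/fail decision depends on the rate.** True. The rate is nevertheless the primary safety result, and with 20 to 35 subjects a single missed event visibly changes it.

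**Conclusion.** The conflict between 8.17 and 8.8 is real and should be resolved. As written, an implanted subject can be exited before day 90. A later major complication is then neither collected nor counted, and the censoring can be informative when the subject breached a risk criterion. This weakens the purpose of SAP 7.1.2 without contradicting it.

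The size is conditional: about 5.0 points per missed event at n = 20 and 2.9 at n = 35. That requires a subject to be implanted, exited early, and then to have a related major complication by day 90. The documents give no frequency for any of these steps. It also assumes that the end of data collection in 8.17 applies to every exit.

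A reader might infer that the bias always favours the device. The arithmetic does not support that: the rate rises only when an event is missed, and it can fall slightly when the exited subject would have had none (95.0% to 94.7% at n = 20).

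**What to change.** In Protocol 8.17:
1. Limit the eligibility exit reason to subjects in whom no EV ICD implant was attempted.
2. State that a violation found after an attempt is reported as a deviation under 8.16, and that a subject with an implanted system stays in follow-up under 8.8.
3. Reconcile the 30-day sentence with 8.8 so that it does not permit exit of subjects who still have the system implanted before the 90-day endpoint is observed. Changing the eligibility reason alone would leave this conflict in place.

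The screen-failure use of the reason is preserved, and SAP 7.1.2 and 7.4 can stand. The cost is a short protocol edit, a matching change to the exit eCRF, and follow-up of any such subjects at visits that are already scheduled.

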8.6.7.9. Unsuccessful Implant Definition

Implant procedure/testing is considered unsuccessful if any of the following occur:

- EV ICD System is not fully implanted
- Defibrillation testing does not meet criteria for success
- R-wave < 1mV for all possible sensing vectors after troubleshooting methods are exhausted

If the subject completes the initial implant procedure without completing the defibrillation testing, the subject may be brought back prior to pre-hospital discharge to complete the defibrillation testing, as outlined in Figure 8.2.

If the EV ICD system is explanted or repositioned after initial implant procedure but prior to pre-hospital discharge, this should be captured on a system modification eCRF. In the event of the EV ICD being permanently explanted, these subjects should be followed and assessed for AEs through 30 days or until procedure or system related AEs have been resolved, at which point subjects can be exited.

An unsuccessful implant procedure, and unsuccessful or incomplete testing (including prolongation of hospital stay by allowing time to minimize transient factors affecting defibrillation) are not considered adverse events; however, any adverse events occurring during an unsuccessful implant attempt (e.g., subject allergy to electrodes used during implant) must be recorded and classified. Subjects with an unsuccessful EV ICD attempt will be followed up through 30 days or until procedure or system related AEs have been resolved, at which point they can be exited.

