12.3.2. Performance Requirements

Performance requirements are not pre-specified for this objective. The endpoint is defined as a subject's first occurrence of a major complication related to the EV ICD system and/or procedure as determined by the independent Clinical Event Committee (CEC) that occurs on or prior to 3-months (90-days) post-implant.

For an adverse event to meet the endpoint, the event must have occurred within 90 days (inclusive) of the EV ICD system implant and be adjudicated by the CEC as being a major complication related to the EV ICD system and/or procedure. Major complications are those complications resulting in:

- Death
- Permanent loss of defibrillation function due to mechanical or electrical dysfunction of the device
- Hospitalization

- Prolonged Hospitalization by at least 48 hours
- System revision (reposition, replacement, explant)

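### Subjects left without a system may exit at about day 30, and Protocol 8.17 as printed extends this to implanted subjects, although the primary safety endpoint is a 90-day rate in all implant attempts

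*Protocol*

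**What the plan says.** **Endpoint.** Protocol 12.3.2 and SAP 7.9.1.2 count the first major complication, adjudicated by the events committee, up to and including day 90. One qualifying outcome is "System revision (reposition, replacement, explant"). Protocol 12.3.4 and 12.3.5, with SAP 7.9.1.4 and 7.9.1.5, estimate the 90-day rate by Kaplan-Meier in all subjects in whom an implant was attempted.

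**Exit.** Four sections bear on when a subject may leave:

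- Protocol 8.6.7.9: "Subjects with an unsuccessful EV ICD attempt will be followed up through 30 days or until procedure or system related AEs have been resolved", after which they can be exited. A permanent explant before discharge is handled the same way.
- Protocol 8.11, for an explant without replacement: "the subject will be exited from the study provided any procedure, system or accessory related adverse events are resolved". No minimum day is given.
- Protocol 8.17: "Subjects who had undergone an implant attempt and have an EV ICD System implanted or had their EV ICD System removed" without replacement "may be exited by phone at the end of 30 days once all system and procedure-related AEs are resolved".
- Protocol 8.8: "All subjects with an implanted EV ICD System will remain in the study and be followed at pre-defined study visits until official study closure".

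**After exit.** Protocol 8.17 adds: "Upon withdrawal from the study, no further study data will be collected". SAP 7.4 censors subjects who leave before a major complication at their exit date.

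**Status of a failed attempt.** Protocol 8.6.7.9 says that an unsuccessful procedure and unsuccessful or incomplete testing "are not considered adverse events; however, any adverse events occurring during an unsuccessful implant attempt" must be recorded.

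**The concern.** There are two separate problems.

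First, 8.17 as printed applies the 30-day exit to subjects who have a system in place, which contradicts 8.8.

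Second, and independently of that wording, the plan allows a foreseeable group to leave well before the endpoint window closes while keeping them in the analysis set. Kaplan-Meier then gives them the day 30-90 risk of subjects who kept the system. That is sound only if leaving is unrelated to later risk. Here exit follows from a failed implant or an explant and from resolution of related adverse events, so the censoring may be informative.

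The bias could go either way. A subject with no system can hardly have a later loss of defibrillation function or a system revision, which would make the reported rate too low. A late procedure-related hospitalization or death would be missed, which would make it too high.

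**Working it through.** **No planned figure to reproduce.** The objective has no hypothesis, power or assumed dropout rate. The check compares the sections and then sizes the effect under stated assumptions.

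**Who is exposed.** An explant caused by a related complication is already an endpoint event, so later exit changes nothing for that subject. The exposed group is failed attempts without an adverse event, and explants not adjudicated as complications. Exit at day 30 leaves 60/90 = 67% of their endpoint window unobserved. Under the 8.6.7.9 alternative (30 days *or* resolution) and under 8.11 (no minimum day), exit could come earlier.

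**Bias formula.** Let S30 be the event-free proportion at day 30, f the share of those event-free subjects who leave, ps the day 30-90 risk of stayers and pl that of leavers.

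- Kaplan-Meier tends to S30 × (1 - ps).
- The true rate is S30 × [(1 - f)(1 - ps) + f(1 - pl)].
- Bias = S30 × f × (pl - ps); a positive value means the reported rate is too high.

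Assumed inputs are S30 = 0.95, ps = 3-5%, pl = 0-10% and f = 5-20%. The documents give no exit rate. For scale only, the first acute study in Protocol 3.1 had 1 defibrillation failure in 14 (7.1%), equivalent to 20/14 = 1.4 to 35/14 = 2.5 subjects here.

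| f | Lowest: pl = 0, ps = 5% | Highest: pl = 10%, ps = 3% |
|---|---|---|
| 20% | 0.95 × 0.20 × (-0.05) = -0.95 points | 0.95 × 0.20 × 0.07 = +1.33 points |
| 1/14 | -0.34 points | +0.48 points |
| 5% | -0.24 points | +0.33 points |

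**Bounds in small samples.** Each unknown outcome is worth 1/35 = 2.9 points or 1/20 = 5.0 points. The rows below use assumed counts, with N the number of attempts and all exits event-free at day 30. The best case gives leavers no events; the worst case gives every leaver one.

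| N | Events by day 30 | Later events seen | Exits | Kaplan-Meier | Best | Worst |
|---|---|---|---|---|---|---|
| 35 | 2 | 0 | 3 | 33/35 = 94.3% | 94.3% | 30/35 = 85.7% |
| 35 | 1 | 1 | 3 | (34/35)(30/31) = 94.0% | 94.3% | 85.7% |
| 20 | 1 | 0 | 1 | 19/20 = 95.0% | 95.0% | 18/20 = 90.0% |
| 20 | 1 | 1 | 2 | (19/20)(16/17) = 89.4% | 90.0% | 80.0% |

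**Literal reading of 8.17.** If every event-free implanted subject were exited at day 30, nobody would be at risk afterwards and the day-90 rate could not be estimated.

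**The case against.** **The implanted-subject wording is clerical.** Protocol 8.8 and 8.11 keep subjects with a system on the normal schedule, and the exit reasons in 8.17 refer to subjects who do not have, or no longer have, a system. This largely stands. The text is not wholly harmless, though. Section 8.6.7.9 counts failed defibrillation testing as unsuccessful without requiring explant, and 8.17 lists that failure as an exit reason, so a subject could leave with the system in place.

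**The plan already protects follow-up.** Exit is permissive, subjects are urged to stay, and Protocol 10.2 follows related events to resolution. This covers events known at exit. It does not detect a new event on days 31-90. Table 16 shows that such events are plausible: implant-site infections rise from 8 at 30 days to 14 at 12 months. Those data are transvenous and run longer, so they show plausibility and not a rate.

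**Late events would be hard to attribute.** Many leavers may receive another ICD, which blurs attribution to the EV ICD procedure. That is fair, but adjudicating attribution is the committee's task and it needs the events to be reported.

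**The effect is small and rests on assumptions.** This stands. No passage supports f = 20%. The 1-in-14 figure comes from an acute study at 35J, whereas this pilot allows repositioning, polarity change and repeat testing. At a 10% risk each, three leavers would all have events with probability 0.1³ = 0.1% if independent. Exact 95% intervals are about 81-99% for 33/35 and 75-99.9% for 19/20, so sampling error dominates. No performance criterion depends on the rate.

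**It may be too late.** The protocol is dated March 2018 with five months' expected enrollment, and the SAP has since been revised to the 2020 ISO standard. Subjects may already have exited, which would leave only the reporting remedy.

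**Conclusion.** The concern holds. The plan estimates a 90-day rate in all implant attempts but permits part of that set to leave at about day 30, under three rules that differ, with nothing collected afterwards and no sensitivity analysis. Independently, 8.17 as printed conflicts with 8.8.

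The expected bias is modest: probably under about half a point, and about one point in either direction only if a fifth of subjects leave. These figures rest on assumed exit shares and late risks, and the sign is unknown. The range left open is wider, because each unascertained subject moves the bound by 2.9 to 5.0 points. In a descriptive study the estimate is the whole result, and SAP 7.8 foresees regulatory submission and external dissemination of the data. Complete ascertainment is therefore worth its small cost. The wording conflict alone would be an editorial correction.

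**What to change.** 1. **Reconcile Protocol 8.6.7.9, 8.8, 8.11 and 8.17.** The 30-day exit should not cover subjects whom 8.8 keeps in the study, and exit timing after a failed attempt or explant should read the same in 8.6.7.9, 8.11 and 8.17.
2. **Ascertain major-complication status to day 90 for every subject with an implant attempt.** The exit telephone contact already allowed in 8.17 can move from day 30 to day 90.
3. **Add to SAP 7.9.1.4** the numbers at risk at days 30 and 90, and best- and worst-case rates for anyone still censored before day 90. The flow diagram in SAP 7.1.1 shows exits by stage but gives no such bounds.

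The cost is a few sentences in the next protocol and SAP versions, plus about 60 more days of passive follow-up and a later call for roughly 1 to 7 subjects (5% of 20 to 20% of 35, assumed). If the subjects concerned have already exited, item 3 is the remedy that remains.
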